## **10.4. Criteria for Evaluation and Statistical Methods**

### **10.4.1. Safety**

Descriptive summaries of the incidence of all AEs, drug-related AEs, SAEs, drug-related SAEs, AEs leading to discontinuation, and deaths will be provided. All AEs and drug-related AEs will be summarized by counts and proportions of subjects having an AE, each AE type, and an AE of each System Organ Class. Serious AEs will be summarized similarly. AEs leading to discontinuation of treatment or the study will be summarized. All reasons for any early discontinuations will be summarized.

Laboratory data will be summarized in relation to normal range values via counts and percentages of subjects below, within, and above the respective normal range, and by summary statistics (N, mean, median, standard deviation, minimum, maximum, 90% confidence intervals, etc.) for baseline, each observed time point, and change from baseline at each observed time point for continuous lab endpoints.

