#### **Minimum Sample Size Calculations**

Sample Size	TRUE underlying AE rate
6 (each rhu-pGSN dose level)	32%
8 (pooled placebo)	25%
12	18%
18	13%
24 (pooled rhu-pGSN doses)	10%

With each sample size presented in the table above, if zero AEs of a certain type (e.g., serious adverse events [SAEs]) are observed, one could be "90% confident" that the TRUE underlying incidence for that AE is at most the percentage indicated above. Thus with 24 healthy subjects, if no SAEs are observed, the probability is 90% that the true underlying incidence of SAEs in healthy subjects administered 5 doses of rhu-pGSN at 6, 12, 18, or 24 mg/kg of body weight is at most 10%.

No data will be excluded from the summary statistics and analyses, and missing data will not be imputed. All subjects given at least part of 1 dose of study drug will be included in the intention-to-treat analysis (full analysis set). As a sensitivity analysis, a per-protocol analysis set excluding subjects who missed doses and/or randomly discontinued the study before the primary Day 7 Visit will be analyzed. The expectation is that all analysis sets will be almost identical.

Descriptive summaries of the incidence of all AEs, drug-related AEs, SAEs, drug-related SAEs, AEs leading to discontinuation, and deaths will be provided. All AEs and drug-related AEs will be summarized by counts and proportions of subjects having an AE, each AE type, and an AE of each System Organ Class. Serious AEs will be summarized similarly. AEs leading to discontinuation of treatment or the study will be summarized. All reasons for any early discontinuations will be summarized.

Laboratory data will be summarized in relation to normal range values via counts and percentages of subjects below, within, and above the respective normal range, and by summary statistics (N, mean, median, standard deviation, minimum, maximum, 90% confidence intervals, etc.) for baseline, each observed time point, and change from baseline at each observed time point for continuous lab endpoints.

Demographics and medical history characteristics will be summarized via counts and percentages of subjects for categorical variables, and by N, mean and standard deviation or median and interquartile range, as appropriate for the distribution of continuous variables.

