### **6.3. Subject Exclusion Criteria**

1. Pregnant or lactating women
2. Acute illness during the month prior to screening
3. Circumstances that may require any medications (including prescription medication, over-the-counter medication, vitamins, or supplements) during the conduct of the study other than acetaminophen
4. Hospitalization during the year prior to screening
5. History of cancer or treatment with systemic chemotherapy or radiation therapy at any time
6. Transplantation of hematopoietic or solid organs
7. History of diabetes mellitus; myocardial infarction, angina, or other cardiovascular disease; stroke or cerebrovascular disease; chronic obstructive pulmonary disease (COPD) or asthma; deep vein thrombosis (DVT)/pulmonary embolism (PE); liver or kidney disease; psychiatric condition; or active or chronic infection
8. Receipt of blood products during the year prior to screening
9. Chronic mechanical ventilation or dialysis
10. Any clinically significant abnormalities in clinical chemistry, hematology, or urinalysis results as judged by the Investigator

11. Any clinically significant abnormalities of vital signs or physical examination findings as judged by the Investigator
12. Positive results for recreational drugs during screening
13. Any other condition deemed by the Investigator as possibly interfering with the conduct of the study

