### **8.1.5. Laboratory Assessments**

Where indicated, handling and shipping clinical laboratory samples to a central laboratory will be outlined in the Laboratory Manual. If a laboratory screening assessment is performed more than 36 hours before initiation of study drug, the test must be repeated within this time frame.

Blood will be collected at the time points specified in [Table 4](#) for safety laboratory evaluations including complete blood count [CBC], prothrombin time (PT), activated partial thromboplastin time (aPTT), creatinine, bilirubin, alkaline phosphatase, creatine phosphokinase [CPK], aspartate aminotransferase [AST], and alanine aminotransferase [ALT] levels.

In addition, urine will be collected at the time points specified in [Table 4](#) for drug screening (e.g., amphetamines, benzodiazepines, cannabinoids, cocaine, and opiates) and urinalysis (dipstick: glucose, protein, red blood cells, white blood cells).

Abnormal laboratory test results considered clinically significant by the Investigator or that require treatment should be reported as AEs in the eCRF.

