## **9. ADVERSE EVENT MANAGEMENT**

### **9.1. Definition of Adverse Events**

#### **9.1.1. Adverse Event (AE)**

An AE is the development of an undesirable medical condition or the worsening of a pre-existing medical condition following or during exposure to a pharmaceutical product, whether or not considered causally related to the product.

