## **9.7. Reporting Adverse Events**

All AEs, serious and nonserious, will be fully documented on the appropriate eCRF. For each AE, the Investigator must provide its duration (start and end dates or ongoing), intensity,

assessment of causality and whether specific action or therapy was required. All AEs occurring during this healthy-volunteer study will be presumed to be related to study drug unless occurring before the study therapy is initiated pending review by the SRC.

All AEs that occur from the signing of the informed consent form (ICF) until the first dose of study drug should be recorded on the AE eCRF page only if the event was related to a study procedure. All other AEs/findings prior to the first dose of study drug should be recorded as medical history on the applicable eCRF page. All AEs occurring from the first dose of study drug until 28 days after the last dose of study drug must be recorded on the AE eCRF.

All SAEs and Grade 4 AEs must be reported to the Sponsor within 24 hours of the Investigator's knowledge. All AEs occurring during this healthy-volunteer study will be presumed to be related to study drug unless occurring before the study therapy is initiated pending review by the SRC. This reporting should be done by faxing/emailing the completed SAE Report Form to the number provided on the SAE Report Form. After the EOS Visit, only new treatment-related SAEs need to be captured on the AE eCRF and reported to the Sponsor.

Investigators must follow subjects with AEs/SAEs until the event has resolved, the condition has stabilized, withdrawal of consent, the subject is lost to follow up or death OR until the EOS Visit, whichever occurs first. New and ongoing treatment-related SAEs should be followed beyond the EOS Visit. If the subject dies, this should be captured as the outcome of the AE unless no link between the AE and the subject death can be established, in which case the AE will be marked as ongoing and the death will be reported as a separate event.

If a subject is lost to follow up, this should be captured accordingly within the AE eCRF and on the follow up SAE report.

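### The below/within/above laboratory table gives marginal counts only, so it cannot show which subjects left the normal range after dosing; a baseline shift table would

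*Combined protocol and SAP*

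**What the plan says.** Section 10.4.1, repeated in the synopsis, plans two kinds of laboratory summary.

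- Categorical: "Laboratory data will be summarized in relation to normal range values via counts and percentages of subjects below, within, and above the respective normal range".
- Continuous: group summary statistics at baseline and at each time point, plus "change from baseline at each observed time point for continuous lab endpoints".

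Neither sets a subject's post-dose category against that subject's baseline category. A table of that kind is planned for antibodies only (section 10.4.3, Day 1 against Day 28, if any subject has antibodies on Day 1).

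Four other provisions bear on the point.

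- Exclusion criterion 10 in section 6.3 removes "Any clinically significant abnormalities in clinical chemistry, hematology, or urinalysis results as judged by the Investigator". Out-of-range values that the Investigator does not judge clinically significant may enter.
- Section 8.1.5 secures a recent pre-dose value: "If a laboratory screening assessment is performed more than 36 hours before initiation of study drug, the test must be repeated within this time frame". Table 4 schedules safety laboratory tests again on Day 7 and Day 28.
- Section 8.1.5 also gives the route from laboratory result to adverse event: "Abnormal laboratory test results considered clinically significant by the Investigator or that require treatment should be reported as AEs in the eCRF".
- Section 9.7 deals with what is found before dosing: "All other AEs/findings prior to the first dose of study drug should be recorded as medical history on the applicable eCRF page".

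Section 10.1.2 defers further detail to a separate SAP, whose text is not part of the document reviewed.

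**The concern.** The protocol's own idea of an adverse event is change within a subject. Section 9.1.1 reads: "An AE is the development of an undesirable medical condition or the worsening of a pre-existing medical condition following or during exposure". The categorical laboratory table measures something else: how many subjects are outside the range, not how many went outside it. Printing the baseline counts beside the post-dose counts does not help, because both are margins of a cross-table that is not shown.

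Small groups make this matter. In a dose group of 6, one subject is 1/6, or 17 percentage points. One carried-over mild abnormality puts that much into the post-dose percentage, and one new abnormality can be cancelled by one that resolves. Outside adverse event reporting, this table is the main summary by category that does not depend on the Investigator's judgement of clinical significance. What is at stake is its usefulness for showing onset.

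**Working it through.** The plan states no figure on this point, so there is none to reproduce.

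**Inputs from the protocol.** There are 6 active subjects per dose level, 24 active in total and 8 pooled placebo (sections 5.1 and 10.2). Laboratory values are taken before Dose #1, on Day 7 and on Day 28 (Table 4, section 8.1.5).

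**Step 1: what the margins allow (no assumption beyond the same n subjects at both visits).** Of n subjects, let b be above range at baseline, d above range post-dose, and k above at both. The number newly above is d − k. Since k lies between max(0, b + d − n) and min(b, d), the number newly above lies between max(0, d − b) and min(d, n − b). For n = 6:

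| b | d | newly above |
|---|---|---|
| 0 | 1 | exactly 1 |
| 1 | 1 | 0 to 1 |
| 1 | 2 | 1 to 2 |
| 2 | 2 | 0 to 2 |
| 3 | 3 | 0 to 3 |

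The same holds for values below range. When nobody is out of range at baseline, the table gives the answer. Otherwise it generally gives only a range.

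**Step 2: how often someone is out of range at baseline.** The protocol gives no rate, so I assume p = 2.5%, 5% or 10% per analyte. The chance of at least one such subject is 1 − (1 − p)^n:

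| n | p = 2.5% | p = 5% | p = 10% |
|---|---|---|---|
| 6 (one dose level) | 14.1% | 26.5% | 46.9% |
| 8 (pooled placebo) | 18.3% | 33.7% | 57.0% |
| 24 (pooled active) | 45.5% | 70.8% | 92.0% |

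**Step 3: illustration for one direction.** I assume a normally distributed analyte, 2.5% of subjects beyond each limit, no drug effect, and a between-subject variance share r, which is then the correlation between baseline and Day 7. Let p11 be the chance of being above range at both times, p01 = 0.025 − p11 the chance of being above at Day 7 only (equal to the chance at baseline only), and p00 = 1 − p11 − 2·p01. In a group of 6 that shows 1/6 at baseline and 1/6 at Day 7:

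- same subject: 6 · p11 · p00^5
- different subjects (one new, one resolved): 30 · p01² · p00^4

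| r | p11 | p01 | p00 | same | different | share different |
|---|---|---|---|---|---|---|
| 0.3 | 0.00237 | 0.02263 | 0.95237 | 1.1% | 1.3% | 53% |
| 0.5 | 0.00462 | 0.02038 | 0.95462 | 2.2% | 1.0% | 32% |
| 0.7 | 0.00827 | 0.01673 | 0.95827 | 4.0% | 0.7% | 15% |
| 0.85 | 0.01269 | 0.01231 | 0.96269 | 6.3% | 0.4% | 6% |

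Given a 1/6-and-1/6 table, a new abnormality is hidden in about 6% to 53% of cases. Such a hidden case occurs in about 0.4% to 1.3% of all tables per analyte, dose group and direction.

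**Step 4: do the continuous summaries fill the gap?** Change from baseline is summarized by group. Its minimum and maximum would expose a large individual change, but not whether a limit was crossed. Dipstick glucose, protein, red cells and white cells are not continuous, so they get no planned comparison with baseline.

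**The case against.** The strongest reply is that the rest of the safety plan already looks at change from baseline. Clinically significant abnormalities are excluded at entry. Pre-dose findings go to medical history. Post-dose abnormalities that are clinically significant or need treatment become adverse events, graded on the toxicity scale and summarized by type and System Organ Class. This stands, and it confines the gap mainly to values the Investigator does not judge clinically significant.

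Three stronger readings are tempting, and the documents do not support them.

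- A reader might infer that the trial cannot tell new laboratory abnormalities from old ones. That is true of this one table. Adverse event reporting makes the distinction for what it captures, and the subject-level data hold the answer for the rest.
- A reader might infer that the primary endpoint is miscounted. It is the incidence and severity of adverse events (sections 4.2.1 and 9), counted through adverse event reporting and not from the normal-range table.
- A reader might pool low and high values and conclude that a new abnormality is hidden in 11% to 70% of 1/6-and-1/6 cases. The planned table keeps below and above apart, so a move from one side to the other would be visible. The figures for one direction are the right ones.

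The minimum and maximum change from baseline also soften the point for continuous analytes, though not for the dipstick. Finally, the separate SAP may already contain shift tables, and reading the counts as made visit by visit is an interpretation, since the text names no other reference. No test, error rate or sample size depends on this table, so the request is for a better display and does not correct an invalid analysis.

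**Conclusion.** The point holds for the categorical laboratory table as the protocol states it. The result in Step 1 is arithmetic: once any subject is out of range at baseline, the planned counts generally leave the number of new abnormalities open, and with groups of 6 the open interval is wide relative to the group. The percentages in Steps 2 and 3 rest on assumed out-of-range rates, normality, the assumed variance share and no drug effect. They show that an ambiguous table is easily misread but that hidden new abnormalities are uncommon in any single table. The practical weight falls on values not judged clinically significant, and most of all on the dipstick items. I would class it as a cheap improvement that leaves the primary adverse event counts unchanged.

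**What to change.** In section 10.4.1 and the synopsis, or in the SAP, add a shift table for each analyte:

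- Rows: baseline category (below, within, above), with baseline defined as the last value before Dose #1.
- Columns: category at Day 7, at Day 28, and worst post-dose.
- For each dipstick item, use normal/abnormal or the dipstick grade as the categories.
- Show each dose level and pooled placebo separately.
- Report the number newly out of range among subjects in range at baseline.

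The counts now planned remain as the margins of this table, so nothing is lost. The cost is a sentence of text and one standard display from data already scheduled, with no new samples, visits or subjects. The small downside is more cells, most of them empty.

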### **10.4.2. Baseline Characteristics**

Demographics and medical history characteristics will be summarized via counts and percentages of subjects for categorical variables, and by N, mean and standard deviation or median and interquartile range, as appropriate for the distribution of continuous variables.

### **10.4.3. Pharmacokinetics and Immunogenicity**

$C_{max}$ ,  $T_{max}$ ,  $T_{1/2}$ ,  $AUC_{0-8}$ ,  $AUC_{0-12}$ , and additionally after Dose #5,  $AUC_{0-24}$  and  $AUC_{inf}$  will be calculated from the pGSN levels measured for Doses #1 and #5. Since the assay measures endogenous pGSN levels as well as exogenous recombinant pGSN, PK parameters will be calculated for values above baseline by subtracting predose pGSN level from each observed concentration. Tables and graphs will be provided.

Antibodies against rhu-pGSN will be assayed from frozen specimens to determine whether the investigational product induces an antibody response in recipients. The frequency of anti-pGSN antibodies with 95% confidence intervals will be provided for Day 1 (predose) and Day 28. If any subjects had antibodies at Day 1, the presence or absence of antibodies at Days 1 and 28 will be summarized in a  $2 \times 2$  table (Day 1 vs. Day 28).

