Two subjects experienced SAEs: 1 SAE was reported in 1 subject who received a single dose of rhu-pGSN, and 2 SAEs were reported in 1 subject who received placebo in the multiple ascending dose phase. One subject who received a single dose of rhu-pGSN had an SAE of pneumonia (Grade 5, not related) after being withdrawn from the study; and 1 subject who received placebo had SAEs of pneumonia (Grade 4, not related) and pulmonary embolism (Grade 5, not related).

Pharmacokinetic analyses showed that the median rhu-pGSN half-life exceeded 17 hours with all dosing regimens. Overall, rhu-pGSN was well tolerated in patients admitted to non-ICU beds with CAP.

**Study BTI-202** was a Phase 2 randomized, double-blind, placebo-controlled study to evaluate the efficacy and safety of rhu-pGSN added to SOC for the treatment of subjects hospitalized with severe COVID-19 pneumonia (NCT04358406) (DiNubile et al., 2022). The study was conducted

in Spain and Romania. Sixty-four subjects with severe COVID-19 pneumonia were randomized 1:1 to receive rhu-pGSN or placebo intravenously in addition to SOC. Standard of care was left to the judgment of the caregivers without restrictions. Three doses of rhu-pGSN 12 mg/kg based on actual body weight were administered at 0, 12, and 36 hours. Of the 61 treated subjects, 54 completed the study, 4 died, and 3 were lost to follow-up. No subject discontinued due to an AE. The primary efficacy endpoint, the proportion of subjects alive without respiratory, hemodynamic, or renal support on Day 14, did not differ between treatment arms: 25 of 30 rhu-pGSN recipients (83.3%) and 27 of 31 placebo recipients (87.1%). Adverse events occurred with similar frequencies in both treatment groups. Most AEs were mild to moderate in severity and related to COVID-19 pneumonia. Serious adverse events were numerically fewer in the rhu-pGSN group than placebo group and all were assessed as unrelated to study drug. No pattern of AEs was discernable in either treatment arm. Two subjects in each group died during the 90-day study, but no deaths were attributable to study drug.

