### 3.5. Rationale for Study and Starting Dose

Given that pGSN is a naturally occurring plasma protein, the risk of drug toxicity related to rhu-pGSN infusion is expected to be low. In healthy primates dosed for 14 days, drug levels were similar to those obtained in human patients with pneumonia after administration of 12 mg/kg without evident toxicities. The doses given to humans have reached 24 mg/kg for 3 consecutive days. No distinctive safety signal was seen in the 2 small BioAegis studies to date; in fact, SAEs were numerically fewer in rhu-pGSN recipients compared to saline-placebo control subjects. However, in Study CBC-101 evaluating sick patients in the ICU administered a previous formulation of rhu-pGSN, 7 of 21 rhu-pGSN and 0 of 7 placebo recipients died ([Table 2](#)). None of the deaths were judged to be related to study drug and were all attributed to the serious underlying conditions of the participants. A post-hoc analysis indicated the rhu-pGSN group had higher acuity scores than the placebo group. All but one subject who died in Study CBC-101 were in the single-dose rhu-pGSN dosing groups.

Efficacy has only been demonstrated in animal models. It is anticipated that in sick patients, pGSN levels would be lower than normal at presentation and that rhu-pGSN administered IV would be consumed more rapidly than in healthy subjects. As such, efficacy in sick patients may require doses higher than used in the earlier clinical trials. Based on the previous human experience, 3 daily doses of 6, 12, and 24 mg/kg of rhu-pGSN were well tolerated in patients with CAP. An accelerated dosing schedule where rhu-pGSN was administered to patients hospitalized with COVID-19 pneumonia as 12 mg/kg at time 0, 12, and 36 hours was also generally well tolerated.

Before treating a larger number of critically ill patients to establish proof of concept in subjects with ALI/ARDS, the Sponsor aims to study the safety, tolerability, and PK of IV rhu-pGSN administered to healthy subjects. The current study is designed to primarily evaluate the safety and tolerability of sequential ascending doses of rhu-pGSN at 6, 12, 18, and 24 mg/kg of body weight, each given 5 times at 0, 12, 36, 60, and 84 hours.

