### **4.2.2. Secondary Endpoints**

- PK for IV rhu-pGSN including, but not limited to:  $C_{max}$ ,  $T_{max}$ ,  $T_{1/2}$ ,  $AUC_{0-8}$ , and additionally after Dose #5,  $AUC_{0-24}$ , and  $AUC_{inf}$  (levels measured on Day 1 within 30 minutes predose, and at 15 minutes and 1, 2, 4, 8, and 12 hours after Dose #1 and on Days 4 and 5 within 30 minutes predose, and at 15 minutes and 1, 2, 4, 8, 12, and 24 hours after Dose #5)
- Presence of anti-rhu-pGSN antibodies at Day 28

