e Subjects will be interviewed to assess any possible AEs daily for 5 days, at 7 ± 1 day after Dose #1, and at 28 ± 3 days after Dose #1 (EOS Visit). Interviews can be done in person or by phone as mutually agreed by the Investigator and subject, but the EOS Visit should be done in person if possible so blood specimens can be collected.

f Study drug will be administered by IV infusion at time 0 (Day 1), 12 hours (Day 1), 36 hours (Day 2), 60 hours (Day 3), and 84 hours (Day 4). Dose 1 will be at time 0, and a window of ±2 hours will be allowed around dosing times for the 2nd and 3rd doses, and ±4 hours for the last 2 doses. Subjects are to be monitored for administration site reactions during an infusion and for 1 hour after its completion.

g Approximately 5 mL volume of blood will be drawn for measurement of pGSN levels on Day 1 within 30 minutes predose, and at 15 minutes and 1, 2, 4, 8, and 12 hours after Dose #1 and on Days 4 and 5 within 30 minutes predose, and at 15 minutes and 1, 2, 4, 8, 12, and 24 hours after Dose #5. Plasma will be obtained after centrifugation and promptly frozen at -20°C for assay in the central lab. A window of ±15 minutes will be allowed around the scheduled times except for the samples collected at 15 minutes postdose which have a window of ±5 minutes. A single sample will be collected anytime on Days 7 and 28.

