## **8.2. Measurement of pGSN Levels and Pharmacokinetic Assessments**

As indicated in [Table 4](#), approximately 5 mL volume of blood will be drawn for measurement of pGSN levels on Day 1 within 30 minutes predose, and at 15 minutes and 1, 2, 4, 8, and 12 hours after Dose #1 and on Days 4 and 5 within 30 minutes predose, and at 15 minutes postdose, and 1, 2, 4, 8, 12, and 24 hours after Dose #5. A window of  $\pm 15$  minutes will be allowed around the scheduled times except for the samples collected at 15 minutes postdose which have a window of  $\pm 5$  minutes. A single sample will be collected anytime on Days 7 and 28.

Plasma will be obtained after centrifugation and promptly frozen at  $-20^{\circ}\text{C}$  for assay in the central lab for analysis of pGSN concentrations. The concentration-time data will be used for the determination of PK parameters: maximum concentration ( $C_{\max}$ ), time to maximum concentration ( $T_{\max}$ ), terminal half-life ( $T_{1/2}$ ), area under the curve from time zero to 8 hours ( $\text{AUC}_{0-8}$ ), area under the curve from time zero to 12 hours ( $\text{AUC}_{0-12}$ ), and additionally after Dose #5, area under the curve from time zero to 24 hours ( $\text{AUC}_{0-24}$ ) and time zero to infinity ( $\text{AUC}_{\text{inf}}$ ).

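### Dose #1 half-life is planned from 12 h of sampling although the reported half-life exceeds 17 h, and the plan does not say whether the Day 7 and Day 28 levels enter the Dose #5 T1/2 and AUCinf

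*Combined protocol and SAP*

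**What the plan says.** Section 10.4.3 names Cmax, Tmax, T1/2, AUC0-8 and AUC0-12, adds AUC0-24 and AUCinf after Dose #5 only, and says that these "will be calculated from the pGSN levels measured for Doses #1 and #5". T1/2 is thus planned for both doses. Section 8.2 has the same structure, as do Section 4.2.2 and the synopsis (which do not list AUC0-12 among the endpoints).

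Sampling is "at 15 minutes and 1, 2, 4, 8, and 12 hours after Dose #1" and, for the last dose, "1, 2, 4, 8, 12, and 24 hours after Dose #5", after a 15-minute sample. Section 8.2 adds: "A single sample will be collected anytime on Days 7 and 28". The Day 7 visit falls "at 7 ± 1 day after Dose #1" (Table 4, footnote e). The sampling list in Section 4.2.2 leaves out Days 7 and 28. Section 8.2 describes them and then assigns the concentration-time data to the PK parameters, without including or excluding those two samples.

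The only half-life given is in Section 3.4.2, for patients with community-acquired pneumonia: "the median rhu-pGSN half-life exceeded 17 hours with all dosing regimens". Section 3.5 expects that in sick patients "rhu-pGSN administered IV would be consumed more rapidly than in healthy subjects", so a healthy volunteer's half-life should be longer if anything. Section 3.3 puts endogenous pGSN at 200-300 mg/L. Section 10.4.3 subtracts a predose level from each observed value and does not say whether this is the Day 1 or the Dose #5 predose level.

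**The concern.** A terminal half-life needs a decline that is large relative to the measurement error. After Dose #1 the level above baseline falls by less than half before Dose #2 is given, and that level is itself a difference between two measured values on a large endogenous background. The error matters most where the increment is smallest, at 6 mg/kg. Precision would therefore differ by dose, and scatter in a table of half-lives from six active subjects per dose could be read as dose dependence or as a change between Dose #1 and Dose #5.

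For Dose #5, two analysts following the same text could report quite different AUCinf values, depending on whether they use the Day 7 level. Characterising the PK profile is the first secondary objective, so the text should settle this.

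**Working it through.** The plan states no extrapolated share and no precision for T1/2, so there is no figure of its own to reproduce.

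**1. Coverage.** Assume mono-exponential decline. Half-lives covered = last sampling time / T1/2.
- Dose #1: 12/17 = 0.71 and 12/24 = 0.50. The fall over 12 h is 1 - 2^(-12/17) = 39% and 1 - 2^(-12/24) = 29%. Section 7.4 allows Dose #2 within ±2 h, so the profile could end at 10 h (10/17 = 0.59).
- Dose #5 to 24 h: 24/17 = 1.41 and 24/24 = 1.00.

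Because 17 h is a figure that the median exceeded, 0.71 and 1.41 are upper limits for a typical patient in that study.

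**2. Extrapolated share of AUCinf after Dose #5** = 2^(-t/T1/2), with the Day 1 predose level subtracted. Day 7 runs from 144 to 168 h after Dose #1 and Dose #5 is at 84 h, so Day 7 is 60 to 84 h after Dose #5 (36 to 108 h with the ±1 day window).

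| Last sample after Dose #5 | T1/2 17 h | T1/2 24 h |
|---|---|---|
| 24 h | 38% | 50% |
| 36 h (earliest Day 7) | 23% | 35% |
| 60 h | 8.7% | 17.7% |
| 84 h | 3.3% | 8.8% |
| 108 h (latest Day 7) | 1.2% | 4.4% |

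**3. Precision of Dose #1 T1/2.** Assumptions not in the documents: one compartment, volume 0.06 L/kg, independent error of CV 5% or 10% on every sample including predose, T1/2 17 or 24 h. The endogenous level is set at 250 mg/L, the midpoint of 200-300. Fit: log-linear regression of baseline-subtracted values on all six postdose samples (0.25 to 12 h). A fit without a decline, or with fewer than three positive values, counts as a miss. Share of simulated subjects within 30% of the true T1/2:

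| T1/2, CV | 6 mg/kg | 24 mg/kg |
|---|---|---|
| 17 h, 5% | 41% | 81% |
| 17 h, 10% | 21% | 50% |
| 24 h, 5% | 33% | 69% |
| 24 h, 10% | 17% | 39% |

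The same fit to all seven Dose #5 samples to 24 h gives about 40-71% at 6 mg/kg and 75-98% at 24 mg/kg.

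**4. How much the Day 7 level can carry.** Just after Dose #5 at T1/2 17 h, the five doses sum to 1 + 2^(-24/17) + 2^(-48/17) + 2^(-72/17) + 2^(-84/17) = 1.60 single-dose increments. One increment at 6 mg/kg is 6/0.06 = 100 mg/L. At 60 h the level above baseline is 100 × 1.60 × 0.087 = 14 mg/L, and at 84 h it is 100 × 1.60 × 0.033 = 5 mg/L. At 24 mg/kg the values are four times as large, about 56 and 21 mg/L. With CV 5% on 250 mg/L, the difference of two samples has an SD of about 12.5 × √2 = 18 mg/L. At 6 mg/kg a single subtracted Day 7 value is therefore mostly noise if T1/2 is 17 h.

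Adding a 72 h point to a log-linear fit of the 8, 12 and 24 h values (6 mg/kg, CV 5%) changes the share within 30% from 46% to 41% at T1/2 17 h, and from 48% to 57% at 24 h. Whether the point helps depends on the true half-life.

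**5. Joint fit.** Fitting total pGSN as a constant endogenous level plus five doses to all samples, including Days 7 and 28, put 78-99% of subjects within 30% at 6 mg/kg and 99-100% at 24 mg/kg under the same assumptions. The data were generated from the fitted model, so this advantage is optimistic.

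**The case against.** A reader might infer that Dose #1 T1/2 cannot be estimated at all. That is too strong: it can be computed, and at 24 mg/kg with 5% error it is often tolerable.

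A reader might also infer that AUCinf is mostly extrapolated. The documents do not support that. At 17 h the share is 38% even without Day 7, and half is reached only at 24 h, which is an assumption; Section 3.5 gives a direction, not a number. Section 8.2 schedules Day 7 and Day 28 under the PK heading and does not bar them, and Section 4.2.2 leaves its parameter list open. What stands for AUCinf is an ambiguity.

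The remaining objections limit the harm. Results are summarised by dose level, so the median of six subjects matters more than single values. For Dose #5 under the same assumptions, that median was within 30% of the truth in 68-96% of simulated groups at 6 mg/kg and in 97-100% at 24 mg/kg. No test of linearity and no comparison of Dose #1 with Dose #5 half-life is planned. Cmax, AUC0-8 and AUC0-12 do not depend on the terminal slope. Section 10.1.2 defers detail to a separate SAP, where a terminal-phase rule could sit. All of this lowers the severity. None of it lengthens the Dose #1 profile or says how the late samples are used.

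**Conclusion.** The point holds in limited form. Dose #1 T1/2 is not reliably estimable from at most 0.71 of a half-life of baseline-subtracted data, and it is worst at 6 mg/kg. The coverage figure uses only the documents' own numbers. The precision figures depend on the assumed volume, error and half-life range.

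For Dose #5, the extrapolated share of AUCinf is about 38% (T1/2 17 h) to 50% (24 h), or about 3-9% to 9-18% with a Day 7 sample taken on the nominal day. The plan leaves the choice open, and simply adding one subtracted Day 7 value does not settle it at the lowest dose. Severity is minor to moderate, since PK is a descriptive secondary objective.

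**What to change.** 1. Remove T1/2 for Dose #1 from Sections 4.2.2, 8.2 and 10.4.3 and the synopsis, or label it exploratory. Keep Cmax, Tmax, AUC0-8 and AUC0-12 for Dose #1.
2. State that the Day 7 and Day 28 levels enter the Dose #5 T1/2 and AUCinf. Prespecify a per-subject joint fit of total pGSN (constant endogenous level plus the five doses at their actual times) to all samples, and show it beside the non-compartmental values.
3. List the extrapolated share of AUCinf for each subject. A fixed cut-off for calling AUCinf unreliable is optional; the documents give no basis for a particular one.

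The cost is protocol and SAP wording and some modelling work, with no new samples or visits. One listed parameter is dropped or downgraded. The joint fit depends on a simple model with a constant endogenous level, so its fit must be shown.
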